7.3. Bone Mineral Density and Bone Biochemical Markers

BMD primary endpoints to be evaluated include:

- Cumulative incidence of at least a 4% decrease from baseline in spine BMD
- Spine BMD (g/cm^2) and change from baseline
- Percent change from baseline in spine BMD (categorical)
- Z-Scores for spine BMD (g/cm^2) and change from baseline (categorical)
- Cumulative incidence of at least a 4% decrease from baseline in whole-body BMD
- Whole-body BMD (g/cm^2) and change from baseline
- Percent change from Baseline in whole-body BMD (categorical)
- Z-Scores for whole-body BMD (g/cm^2) and change from baseline (Categorical)

Cumulative incidence of at least a 4% decrease from BL in spine and whole-body BMD will be summarized by monitoring group and study week for each randomization age group (12-14 years, 15-17 years). No inferential statistics will be computed.

The percent change from BL in spine BMD and in whole-body BMD will also be summarized categorically by monitoring group and overall for each study week using the following categories: ≤ -4 , > -4 to ≤ -2 , > -2 to ≤ 0 , > 0 to ≤ 2 , > 2 to ≤ 4 , > 4 , and Missing. No inferential statistics will be computed.

Z-score and changes from BL in z-score will also be summarized categorically (n, mean, standard deviation, median, Q1, Q3, minimum and maximum) by monitoring group and overall for each study week. No inferential statistics will be computed.

Spine BMD and whole-body BMD clinical status will also be summarized categorically by monitoring group and overall for each study week using the following categories: > -1 , -1 to -2 , < -2 , Total, and Missing. No inferential statistics will be computed.

Serum bone biochemical markers will be summarized (n, mean, standard deviation, median, Q1, Q3, minimum and maximum) by monitoring group and overall for each study week, as well as the changes from BL. In all cases of serum bone biochemical markers, no inferential statistics will be computed.

The following bone biochemical markers as previously mentioned in the laboratory results section will be assessed:

- N-telopeptide (nmol BCE/L)
- C-telopeptide (ng/mL)
- Serum osteocalcin (ng/mL)

- Bone-specific alkaline phosphatase ($\mu\text{g/L}$)
- Serum PTH (pg/mL)
- Vitamin D (25-hydroxy, [ng/mL])

Baseline, and change from baseline in bone biochemical markers will be summarized by treatment group and visit using the Safety Analysis Set. The change from baseline in bone biochemical markers will be compared using the Wilcoxon rank-sum test up to Week 48, where applicable. Supportive listings for bone biochemical marker measurements will also be provided. For fasting serum and fasting creatinine, only measurements taken when subject was confirmed to be fasting will be reported.

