8.6.4. Other Safety Evaluations: Analyses of BMD

Cumulative incidence of at least a 4% decrease from baseline in BMD (spine BMD and whole body BMD) using time-to-event methodology will be summarized and compared between treatment groups using 95% confidence intervals for difference in person time rates.

The percent change from baseline in BMD (spine BMD and whole body BMD) will be summarized over time and compared between treatment groups using the Generalized Linear Model. Lumbar spine and whole body z-scores (derived from DEXA-derived BMD assessments) and the changes in z-scores from Baseline will be summarized.

BMD (via DEXA scan) and serum bone biochemical markers will be summarized over time. Changes from study baseline in bone biochemical markers will also be summarized after adjusting for potential confounders such as age and gender..

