1.1. Study Objectives

Primary Study Objectives
	
To characterize the long term (i.e., 96 weeks of follow up) bone safety profile of open-label TDF treatment in adolescents with CHB. This includes prospectively evaluating and comparing the bone mineral density (BMD) changes between CHB- infected adolescents 12 to < 18 years of age treated with TDF in European treatment centers who were assigned to one of two schedules for renal and bone laboratory monitoring and BMD measurements. Primary study endpoint was the percent changes in BMD from Baseline through study Week 96.

Secondary Study Objectives
	
 • To document all serious adverse drug reactions (SADR) and all renal- and bone-related adverse events (AEs), including renal and bone laboratory abnormalities • To determine the time to diagnosis of renal and bone AEs and document the resulting patient management and outcome(s) • To assess the clinical management and outcomes of renal- and bone-related \geq Grade 3 laboratory parameters and clinical SAEs. • To assess the efficacy and tolerability of TDF in adolescents with CHB infection • To assess the use of oral vitamin D, calcium and phosphate supplementation and explore the association between supplement use and rates of bone and renal AEs • To describe the demographics and disease characteristics of adolescents with CHB infection treated with TDF.

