1.4. Sample Size and Power

Planned Sample Size	100 subjects (50 subjects to one of two monitoring groups)
Power Statement	
The study employed two monitoring protocols which specified the same laboratory and imaging tests for bone and renal markers and differed in the frequency of testing. Group 1 receives more frequent monitoring which is protocol-defined or SmPC specified, and Group 2 subjects are monitored according to a less frequent DXA schedule for BMD and followed the local standard of care for renal monitoring. It is hypothesized (H_0) that there would have been no difference in the timing, management, or subject outcomes resulting from renal or bone AEs among the two monitoring regimens. With a one-tailed test of $\alpha=0.05$, and assuming a non-inferiority margin of 0.10, the study had at least 80% power to detect a difference between the monitoring regimens beyond the specified margin of non-inferiority.
 
The primary safety endpoint is cumulative incidence of at least a 4% decrease from study baseline (BL) in spine bone mineral density (BMD) through Week 96.
 
The null hypothesis is the difference (Group 1 – Group 2) is equal to 0.
 
The alternative hypothesis is the difference (Group 1 – Group 2) is not equal to 0.

Actual Enrollment and Impact on Power	
The study failed to achieve its targeted enrollment of 100 patients, 50 per monitoring group. The study was discontinued as a result of the recent approval of Tenofovir alafenamide fumarate (TAF) medicine which offers a safer treatment option for CHB patients and due to low subject enrollment after the CHMPs assessment of the 18 month interim enrollment report. At the time of its closure the study enrolled 30 patients, 15 per monitoring group. The total enrolled subjects are underpowered to statistically detect differences in outcomes between monitoring groups.

--	--

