4.2. Disposition of Subjects

A summary of subject disposition will be provided by monitoring group and overall. This summary will present the number of subjects screened, randomized, included in the safety analysis set, and the number and percentage of subjects meeting the following criteria:

- Completed the study treatment period,
- Did not complete the study treatment period (with summary of reasons for not completing the study treatment period),
- Completed the study (includes the study treatment period), and
- Did not complete the study (with summary of reasons for not completing the study).

The denominator for the percentages of subjects in each category will be the number of subjects in the Safety Analysis set.

No inferential statistics will be generated. A data listing of reasons for premature study treatment/study discontinuation will be provided. The most recent, non-missing primary and key secondary endpoint values prior to discontinuation will be included in this listing.

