7.2.2.3. Summaries of Laboratory Abnormalities

The following summaries (number and percentage of subjects) of laboratory abnormalities will be provided by monitoring group (subjects categorized according to most severe abnormality grade), where applicable:

- Treatment-emergent laboratory abnormalities
- Treatment-emergent marked laboratory abnormalities

For all summaries of laboratory abnormalities, the denominator is the number of subjects with non-missing post-baseline values in the given study period. A listing of treatment-emergent Grade 3 or Grade 4 laboratory abnormalities will be provided.

Incidence of ALT flare and post-treatment exacerbation of hepatitis is defined as follows:

- Serum ALT $> 2 \times$ study BL and $> 10 \times$ ULN, with or without associated symptoms

OR

- Confirmed ALT elevation (defined as 1-grade shift [ie, increase] or $2 \times$ previous value) with confirmed changes outside of the normal range in other laboratory parameters suggestive of worsening hepatic function (total bilirubin ≥ 2 mg/dL above study BL, abnormal prothrombin time ≥ 2 seconds over BL or international normalized ratio [INR] ≥ 0.5 over BL, abnormal serum albumin ≥ 1 g/dL below BL or elevated serum lactate levels [if available], defined as $2 \times$ ULN).

Summaries (number and percentage of subjects) of treatment-emergent, on-treatment laboratory abnormalities will be provided by monitoring group and overall, with the following modifications for the creatinine summaries:

Confirmed (defined as 2 consecutive visits) increase in serum creatinine of 0.3 mg/dL above BL

Confirmed (defined as 2 consecutive visits) increase in serum creatinine of 0.5 mg/dL above BL.

A confirmed laboratory results is defined as either being present at 2 consecutive visits or at the last visit. If the first of 2 consecutive results is on-treatment and the second is off-treatment, then the result is considered confirmed.

For all summaries of laboratory abnormalities, the denominator is the number of subjects in the Safety Analysis Set.

Hepatic flares will be summarized by monitoring group and overall.

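### Percent change in BMD, which SAP 1.1 names as the primary endpoint, is reported only in bands; the 4% loss incidence lacks an estimator and a missing-scan rule; SAP 7.8 omits the changes from the protocol

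*SAP*

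**What the plan says.** The SAP labels more than one BMD quantity as primary. Section 1.1 states: "Primary study endpoint was the percent changes in BMD from Baseline through study Week 96". Section 1.4 states: "The primary safety endpoint is cumulative incidence of at least a 4% decrease from study baseline (BL) in spine bone mineral density", through Week 96. Section 7.3 then lists eight BMD primary endpoints: four for the spine and the same four for the whole body.

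Section 7.3 treats them as follows.

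- **Percent change:** "The percent change from BL in spine BMD and in whole-body BMD will also be summarized categorically by monitoring group and overall". There are six bands with cut points at -4, -2, 0, 2 and 4, plus Missing. Tables 26.2 and 27.2 in Appendix 3 are subtitled as categorical summaries.
- **Absolute change (g/cm²):** listed for both sites, with no paragraph on how to summarize it and no table in the 26 and 27 series.
- **Z-score change:** "Z-score and changes from BL in z-score will also be summarized categorically (n, mean, standard deviation, median, Q1, Q3, minimum and maximum"). The word used is categorical, but the statistics named are continuous.
- **Incidence of at least 4% loss:** by monitoring group, study week and age group. No estimator, denominator or censoring rule is given.

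Protocol 8.6.4 planned more: "The percent change from baseline in BMD (spine BMD and whole body BMD) will be summarized over time and compared between treatment groups" with a Generalized Linear Model. For the 4% incidence it planned time-to-event methods with a 95% confidence interval for the difference in person-time rates. Protocol 8.3 left the missing-data rule for the primary endpoint to the SAP. SAP 3.6 says only that missing values are generally not imputed, and the two missing-data rules in SAP 3.9 concern efficacy.

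SAP 7.8 states that the protocol's safety analysis was not altered, then mentions a shift to available exposure. SAP 2.1 says the data will be described by group and pooled where possible.

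**The concern.** Bone markers (SAP 7.3) and body weight (SAP 7.4) receive n, mean, SD and quartiles, but the endpoint that SAP 1.1 calls primary does not. Protocol 1.2.3.1 reports that mean spine BMD rose in the earlier adolescent trial, so subjects may collect in the open band above 4%, where the size of the gain cannot be read.

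The 4% incidence is the one BMD proportion for which the protocol supplies an outside figure. With most subjects stopping early, its value depends on whether a subject with no follow-up scan counts as event-free, is excluded or is censored. The choice is not self-evident. For laboratory abnormalities SAP 7.2.2.3 first says "the denominator is the number of subjects with non-missing post-baseline values in the given study period", and later in the same section uses the whole Safety Analysis Set. Nor do the groups have equal chances of detection: Group 1 has four scheduled post-baseline scans and Group 2 has two.

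A reader who relies on SAP 7.8 would take the protocol's analyses to be intact.

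**Working it through.** **1. Protocol and SAP side by side**

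| Item | Protocol 8.6.4 | SAP 7.3 | Listed in SAP 7.8? |
|---|---|---|---|
| Percent change | Summary over time; Generalized Linear Model | Six bands plus Missing | No |
| At least 4% loss | Time-to-event; 95% CI for difference in person-time rates | By group, week and age group; no estimator, no interval | No |
| Absolute change | Not named | Listed as primary; no summary stated | A SAP gap, not a protocol change |
| Unscanned subjects | Rule left to the SAP (8.3) | No rule | A SAP gap, not a protocol change |

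**2. The plan's own benchmark.** Protocol 8.9 gives 5.8% (1.2-15.9%) with at least 4% loss on TDF at Week 72. Protocol 1.2.3.1 gives 52 subjects on TDF. 3/52 = 5.8%, and the exact (Clopper-Pearson) interval is 1.2-15.9%, so the figure reproduces.

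**3. Effect of the denominator.** The documents give 30 enrolled and two completers. They do not give the number with a follow-up scan, so 20, 15 and 10 are assumptions. For zero events the exact upper limit is 1 - 0.025^(1/n).

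| Denominator | Upper 95% limit, 0 events | 1 event (exact 95% CI) |
|---|---|---|
| 30 | 11.6% | 3.3% (0.1-17.2%) |
| 20 | 16.8% | 5.0% (0.1-24.9%) |
| 15 | 21.8% | 6.7% (0.2-31.9%) |
| 10 | 30.8% | 10.0% (0.3-44.5%) |

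The zero-event limit first falls below 5.8% at n = 62. With 30 enrolled, no denominator rule makes zero events exclude the earlier rate. The rule governs how the result reads, not whether it is conclusive.

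**4. Information lost by banding.** The documents give no mean or SD for percent change, so both are assumed (normal, SD known). The share of information on the mean that the bands keep is the sum over bands of d²/p, where p is the band probability and d the difference in standard normal density between its edges.

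Example, mean 6% and SD 4%: the standardized cut points are -2.5, -2, -1.5, -1 and -0.5, and the six terms are 0.050 + 0.080 + 0.129 + 0.138 + 0.081 + 0.179 = 0.66.

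| Mean gain | SD 4% | SD 8% |
|---|---|---|
| 2% | 0.89 | 0.82 |
| 3% | 0.86 | 0.81 |
| 6% | 0.66 | 0.73 |
| 10% | 0.28 | 0.56 |

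The loss is small at small gains and large only if gains are well above 4%.

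**5. Effect of unequal scan schedules.** I simulated 400,000 subjects with a linear trend (96-week mean 2% or 4%, SD 3%) and independent scan error of 1-2% at each scan, including a shared baseline error. All of these are assumptions. An event is a measured loss of at least 4% at any scheduled scan.

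| Mean, scan error | Scans at 24/48/72/96 | Scans at 48/96 |
|---|---|---|
| 2%, 1% | 4.3% | 3.7% |
| 2%, 1.5% | 9.1% | 6.5% |
| 2%, 2% | 16.5% | 10.7% |
| 4%, 1% | 1.1% | 0.9% |
| 4%, 1.5% | 3.7% | 2.2% |
| 4%, 2% | 9.0% | 4.8% |

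The same subjects show 1.2 to 1.9 times as many events under the Group 1 schedule, so an any-scan incidence is not comparable between groups.

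**The case against.** The study closed early with 30 subjects. SAP 1.4 and 2.1 say openly that it cannot compare the groups and that the data will be described. That justifies dropping the model and the between-group intervals, and I do not ask for their return. It does not explain leaving out a mean and SD, which need no inference.

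Z-score change already has a mean and SD, the lowest band shows weekly losses of 4% or more, and the Missing row shows how many were not scanned. All of that stands, and so no safety signal is lost. The documents also give no percent-change result from the earlier trial, only Z-score changes and the 4% proportion, so they do not themselves supply a mean percent change for comparison. Confidence intervals for single groups are an addition to the protocol and a matter of preference. Appendix 3 omits other outputs that the text promises, so a missing table is weak evidence alone. For absolute change, the method is missing from the text of 7.3 as well.

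Three stronger readings are tempting, and the documents do not support them.

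- **Group 2 subjects who stop early get no DXA.** Protocol 6.4.3 makes the Week 24 and 72 scan a Group 1 procedure. Protocol 6.4.4 and 6.4.6 use the same early-discontinuation wording with a scan for both groups, so the text is at most ambiguous.
- **Follow-up BMD values go unlisted.** SAP 7.3 promises listings for bone markers ("Supportive listings for bone biochemical marker measurements will also be provided") and Appendix 3 shows none for BMD. But Protocol 8.2 says all individual data will be listed, and SAP 4.2 adds for discontinuations: "The most recent, non-missing primary and key secondary endpoint values prior to discontinuation will be included in this listing".
- **Incidence rates for renal and bone AEs were dropped.** SAP 7.1.7, on additional AE analyses, is redacted, so this cannot be known.

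**Conclusion.** The point holds as an incomplete and partly undefined report of the BMD endpoints, together with an inaccurate statement of changes. It is worth fixing because the repair is cheap.

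Three parts rest on the text alone: percent change has only bands; absolute change has no summary and the 4% incidence no estimator or missing-scan rule; and SAP 7.8 is untrue against Protocol 8.6.4. On the last, the model and between-group intervals have been removed. The time-to-event method is unspecified rather than shown to be replaced, since SAP 7.3 still speaks of cumulative incidence.

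The sizes rest on assumptions. The banding loss (11-19% of the information at gains of 2-3%, 27-72% at 6-10%) depends on an assumed SD of 4-8%. The spread from 3.3% to 10.0% for a single event depends on an assumed number scanned. The detection ratio of 1.2 to 1.9 depends on the assumed trend and scan error.

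SAP 1.1, 1.4 and 7.3 also differ on which BMD endpoint is primary, so both percent change and the 4% incidence need a complete specification.

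**What to change.** 1. **Continuous summaries.** In SAP 7.3 and the Table 26 and 27 series, add n, mean, SD, median, Q1, Q3, minimum and maximum for percent and absolute change in spine and whole-body BMD, by group and overall at each scan week. Keep the bands. A descriptive 95% interval is optional; p-values are not needed.
2. **Incidence of at least 4% loss.** Use as denominator the subjects with a baseline scan and at least one post-baseline scan, and show the number scanned at each week. Report all available scans as the main safety figure. Add a version limited to Weeks 48 and 96 for any comparison between groups. That version should not be the main figure, because in a study where most stopped early it would leave out losses seen only at other scans.
3. **SAP 7.8.** List the analyses of Protocol 8.6 and 8.6.4 that were dropped or changed, and give the reason.

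The cost is a few table rows on data already collected and some SAP wording. No visits, tests or hypothesis tests are added, and the descriptive intent of SAP 2.1 is kept.

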- DEXA: every 48 weeks from Baseline to Week 96 (3 scans)
- Serum bone chemistry (i.e., calcium, phosphorus, vitamin D levels (25-hydroxy and 1,25 dihydroxyvitamin), PTH, osteocalcin, bone-specific alkaline phosphatase, N and C telopeptides): every 48 weeks
- Serum renal chemistry and urinalysis according to local standards of care

Subjects who permanently discontinue Tenofovir DF will be asked to return for an end of treatment visit within 72 hours of the last dose of Tenofovir DF. Subjects who permanently discontinue Tenofovir DF will be followed for 24 weeks off treatment or up to initiation of local standard of care treatment, whichever occurs first.

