2. TYPE OF PLANNED ANALYSIS

2.1. Final Analysis

Final Analysis includes the time period from the first date of OL TDF dose through and including the date of last OL TDF dose plus 30 days. As a result of early study termination (FPFV July 2015 to LPLV April 2018) only two patients completed 96 weeks of observation on TDF treatment for HBV, the primary study objective to characterize the safety profile (renal and bone adverse outcomes) of subjects will be summarized based on available TDF exposure time. The assessment of efficacy and tolerability of TDF will be described. As most of the enrolled subjects were unable to complete the target observation period of 96 weeks, the final analysis will be unable to provide meaningful evidence to suggest whether enhanced or standard of care renal and bone monitoring frequencies between Group 1 and Group 2 offer early detection and mitigation of renal or bone adverse events. Instead, the data will be described by monitoring group and pooled together where possible.

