7.2. Laboratory Evaluations

Selected laboratory data (using conventional units) will be summarized by the observed data and change over time. Missing laboratory results for safety summaries will not be imputed. In all cases for laboratory evaluations, no inferential statistics will be computed.

Glomerular filtration rate (estimated creatinine clearance) will be calculated via statistical programming at each visit

(a) using Schwartz formula for subjects ages 12–18 years (ie, 12 to < 19) as follows:

$$\text{Schwartz formula (mL/min/1.73 m}^2\text{)} = k \times L/\text{Scr}$$

k is a proportionality constant,

k=0.55 for adolescent females 12-18 years old; and

k=0.70 for adolescent males 12-18 years old

L is height in centimeters (cm); and

Scr is serum creatinine (mg/dL)

(b) using Cockcroft-Gault equation for age ≥ 12 years as follows:

$$\frac{(140 - \text{age in years}) (\text{body weight [kg]})}{(72) (\text{serum creatinine [mg/dl]})}$$

[Note: multiply estimated rate by 0.85 for women; use actual body weight]

Creatinine clearance (CLcr) summaries will be provided by Schwartz and Cockcroft-Gault separately.

Summaries and data listings will use the Safety Analysis Set. For subjects who discontinue prior to the final week for the given analysis, all on-treatment laboratory data collected on or before the date of last dose + 7 days will be included in tabular summaries. Laboratory data prior to the first dose date of TDF will be included in data listings.

Summaries of laboratory data will be provided for the safety analysis set. No inferential statistics will be generated.

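### SAP 7.3 both rules out inferential statistics for the bone markers and orders Wilcoxon tests on them up to Week 48, with no alpha, sidedness or multiplicity rule

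*SAP*

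**What the plan says.** SAP 7.3 first sets out descriptive summaries of the serum bone markers by monitoring group and overall, and closes that paragraph with "In all cases of serum bone biochemical markers, no inferential statistics will be computed". It then lists six markers: N-telopeptide, C-telopeptide, osteocalcin, bone-specific alkaline phosphatase, PTH and 25-hydroxy vitamin D. The paragraph after the list states that change from baseline in these markers "will be compared using the Wilcoxon rank-sum test up to Week 48, where applicable". SAP 7.2 has its own exclusion: "In all cases for laboratory evaluations, no inferential statistics will be computed".

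The SAP's account of the terminated study points the same way as the exclusions. SAP 1.4 reports: "At the time of its closure the study enrolled 30 patients, 15 per monitoring group", and adds: "The total enrolled subjects are underpowered to statistically detect differences in outcomes between monitoring groups". SAP 2.1 concludes: "Instead, the data will be described by monitoring group and pooled together where possible".

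For Group 2, Protocol 3.2 schedules the bone chemistry panel, including "osteocalcin, bone-specific alkaline phosphatase, N and C telopeptides): every 48 weeks". SAP 1.2 gives the visits as Baseline, Week 48 and Week 96.

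Protocol 8.6 prescribes a Wilcoxon rank-sum test between monitoring groups for continuous safety data, laboratory data included. SAP 7.8 declares that the protocol's safety analysis is unaltered.

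**The concern.** A rank-sum test is inferential, so a programmer cannot obey both sentences of SAP 7.3. The qualifier at the end of the Wilcoxon sentence does not help, because the exclusion covers all cases. If nothing changes, someone will settle the question at the analysis stage, in an open-label study, possibly after seeing the data.

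If the tests are run, supportive markers receive p-values while the primary BMD endpoints, for which SAP 7.3 also rules out inference, receive none. No significance level, sidedness or multiplicity rule is given for these tests. SAP 3.5 waives alpha adjustment on the ground that there is no interim efficacy analysis, which does not address testing several markers at once. One nominally significant marker among six could be read as a monitoring-group effect, although SAP 2.1 says the data cannot inform that comparison.

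**Working it through.** **Which comparisons are scheduled.** Group 1 has markers at Baseline and Weeks 24, 48, 72 and 96; Group 2 at Baseline and Weeks 48 and 96 (SAP 1.2 and Appendix 1). Up to Week 48 the only post-baseline visit common to both groups is Week 48. Six markers at one visit give 6 tests.

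**Plan's own figure.** There is none to reproduce. The SAP states no error rate or power for these tests. The 80% power in SAP 1.4 refers to 50 per group and a non-inferiority margin of 0.10, which is a different comparison.

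**Chance of at least one false positive.** Assume two-sided 5% per test (the SAP gives no level) and no true group difference.

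- Independent markers, nominal level: 1 − (1 − 0.05)^6 = 1 − 0.735 = 26.5%. Expected number of false positives: 6 × 0.05 = 0.3.
- Exact Wilcoxon at 15 v 15, attained size 0.0453: 1 − (1 − 0.0453)^6 = 24.3%.
- Correlated markers, by simulation at 15 v 15 with the exact test: 22.5% at a common correlation of 0.3, 19.0% at 0.5 and 16.3% at 0.7.

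The documents do not say how many subjects have Week 48 markers; 15 per group is the maximum. With fewer subjects the exact size changes. At 8 v 8 it is 0.0499, giving 26.4% under independence; at 5 v 5 it is 0.0317, giving 17.6%.

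**What a single test could detect.** Simulated power for normal data, exact two-sided test at 5%:

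| Shift (SD) | 15 v 15 | 8 v 8 |
|---|---|---|
| 0.5 | 24% | 15% |
| 0.8 | 53% | 31% |
| 1.1 | 80% | 51% |

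Even with complete data, only a shift of about 1.1 SD reaches 80% power, which agrees with the SAP's own description of the study as underpowered.

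**If a multiplicity rule were added.** Bonferroni over six markers gives 0.05/6 = 0.0083 per test.

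**The case against.** The strongest counter-argument is that the Wilcoxon sentence is the one that agrees with the protocol. Protocol 8.6 prescribes that test for continuous laboratory data, and SAP 7.8 says nothing was altered. On that view the exclusions in SAP 7.2 and 7.3 are the undeclared departure, and an exploratory Week 48 comparison is a legitimate repair. This stands in part: deletion is not the only valid answer. It also shows that SAP 7.8 is wrong whichever sentence governs, because SAP 7.2 has already dropped the protocol's tests for laboratory data.

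It is also fair to say that little depends on this. The titles of Tables 22.1 to 22.6 in SAP Appendix 3 mention only values and change from baseline (though titles alone do not exclude p-values), and both groups take the same drug.

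Four stronger readings are tempting, and the documents do not support them:

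- *That the tests will produce a chance finding.* At 26.5%, roughly three times in four there is none.
- *That low power raises the false-positive rate.* It does not. The risk comes from several unadjusted tests; low power makes a significant result less credible.
- *That bone markers would be the only outcomes with p-values.* SAP 6.1 still names a Fisher exact test and SAP 6.3 a Mantel-Haenszel test for efficacy, although both sections also turn to description.
- *That Week 24 would be tested too.* Twelve tests would give 1 − 0.95^12 = 46.0%, but Group 2 has no scheduled markers then. If an early leaver completes the next visit's assessments, as the layout of Protocol 6.4 suggests, the first exit visit with Group 2 bone chemistry is the Week 48 set, for those leaving after Week 36. Apart from the ±7-day tolerance, such samples fall after Day 252, in the Week 48 window of SAP Table 3-2 (Days 253 to 420). A more literal reading of the exit rules, or unscheduled sampling, could put Group 2 data in the earlier window, but the documents do not show that any exist.

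**Conclusion.** The plan is wrong as written: SAP 7.3 contradicts itself on the same markers, and SAP 7.2 sides with the exclusion. That conclusion rests on the text alone. The statistical consequence is a risk of at least one chance finding of up to about 26% for six tests at Week 48. This assumes 5% per test, independence and no true difference; about 16% to 24% is more realistic with correlated markers or the exact test size. Importance is low, because the markers are supportive and SAP 1.4 and 2.1 already disclaim inference between groups. Those two sections are the reason to resolve the conflict in favour of description.

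**What to change.** Delete the Wilcoxon sentence from SAP 7.3 and keep the summaries already specified there (n, mean, SD, median, quartiles, minimum and maximum, by group and overall). In SAP 7.8, replace the statement that the protocol's safety analysis is unaltered with one saying that the protocol 8.6 Wilcoxon tests on continuous laboratory and bone-marker data were dropped because of early termination.

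If the sponsor prefers to keep the test, restrict it to Week 48, label it exploratory, state alpha and sidedness, say whether the six tests are adjusted, and amend the exclusions in SAP 7.3 and 7.2 to match. SAP 7.8 still needs correcting for the other laboratory tests.

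The cost of the preferred repair is two text edits, with no new data or programming. The downside is the loss of a protocol-specified comparison that had little power.
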